#### **4.5 Study Procedures**

Detailed Schedules of Procedures are presented in **Table 5** SPR Trial Stage Schedule of Procedures and **Table 6** SPR Implant Stage Schedule of Procedures below. In addition, specific details regarding each study visit are described in Sections 4.5.1 through 4.5.3 below. In addition, Study Visit Windows are detailed in Section 4.6 below.

**Table 5. Schedule of Procedures- SPR TRIAL STAGE**

	BASELINE	SHAM PERIOD	SHAM/ TRIAL	TRIAL STIMULATION	FOLLOW-UP
Assessment / Procedure	Visit 1 (Baseline)	Visit 2 (Trial Stage Procedure)	Telephone Call #1 (1-week Sham)	Telephone Call #2 (2-weeks Sham)	Telephone Calls #3-7 (1-week Trial Stim ON)
Informed consent obtained	X – Trial Stage			Visit 4 (End of sham period/ Turn Trial Stim ON)	Visit 5 (End of Trial Stim/End of Trial Stage)
Verify General Inclusion/Exclusion	X				Visit Post-5 (Trial Stage 1-week Follow-up visit)
BPI Short Form	X				Telephone Calls #8-2 (Trial Stage Follow-up calls)*
MMSE	X				
TNR measured, pregnancy test	As needed				
Pain-free passive ROM	X		X		X
PGIC	X		X		X
BDI-II	X		X		X
SF-36v2	X		X		X
Economic Survey	X				
SULCS	X		X		
QST testing	X-optional		X-optional		X-optional
Trial System Procedure	X				
Stimulation turned ON/Programming	X-Initiate sham		X-Terminate sham		
Inspect Percutaneous Exit Site	X		X		X
Subject Trial Stage Satisfaction Survey Administered					
Assess Adverse Events	X	X	X	X	X
Assess Subject Compliance			X		X
Remove Trial Lead				X	
Assess effectiveness of Blinding		X	X	X	

Table 6, Schedule of Procedures- SPR IMPLANT STAGE

SPR IMPLANT STAGE													
Assessment / Procedure	Visit Pre-6 (Implant Stage Eligibility)	Visit 6 (Implant Stage Procedure)	Visit 7 (1-week Post-Implant/ Turn IPG Stim ON)	Telephone Call #5 (1-week IPG Stim ON)	Telephone Call #6 (2-weeks IPG STIM ON)	Visit 8 (3-weeks IPG Stim ON)	Visit 9 (6-weeks IPG Stim ON)	Visit 10 (12-weeks IPG Stim ON)	Visit 11 (6-Months IPG Stim ON)	Visit 12 (9-Months IPG Stim ON)	Visit 13 (12-Months IPG Stim ON)	Visit 14 (24-Months Post-IPG Stim ON)	Visit 15 (36-Months IPG Stim ON)
Informed consent obtained	X - Implant Stage												
Verify General Inclusion/Exclusion	X												
BPI Short Form													
MMSE	X												
INR, pregnancy tests	As needed												
Implant Stage Procedure		X											
INR													
Pregnancy Test													
BPI Short Form			X-Q3 only	X									
Pain-Free PROM				X									
PGIC					X								
BDI-I						X							
SF-36v2							X						
SULCS	X						X						
QST	X-optimal							X-optimal					
Turn ON IPG Stim		X											
IPG Programming	X	X-As needed		X-as needed									
Inspect Implant Sites		X			X		X		X		X		
Subject Implant Stage Administered													
Assess Adverse Events	X	X	X	X	X	X	X	X	X	X	X		
Assess Subject Compliance						X	X	X	X	X	X		
Assess Recharge History						X	X	X	X	X	X		

#### **4.5.1 Baseline (Visit 1)**

Potential study participants will be screened for eligibility from a pool of candidates with post-stroke shoulder pain and recorded in the Subject Screening Log. Patients meeting all general eligibility criteria will be asked if they are interested in participating in the study. The Informed Consent Form will be reviewed with the potential subject to ensure that the risks and benefits of study participation are fully understood. The Informed Consent for this study consists of two documents: the Trial Stage Consent Form and the Implant Stage Consent Form. Prior to any data collection, subjects who agree to participate in the study must sign the Trial Stage Informed Consent Form and will be asked to read the Implant Stage Consent Form such that the risks of participating in both phases of the study are presented to the subject. The Trial Stage Informed Consent Form may be signed up to 30 days prior to the SPR Trial Stage procedure. Prior to the Implant Stage procedure, the study participants who qualify to progress onto the Implant Stage (and agree to continue to the Implant Stage) will be asked to review and sign the Implant Stage Consent Form such that the risks of participating in that phase of the study are clearly understood.

Subjects will then be screened for their cognitive ability to participate in the study and complete the required surveys. The Mini Mental Status Exam (MMSE) will be administered to determine the subject's cognitive ability to participate in the study. The MMSE has been validated as a cognitive function survey instrument and has been widely used in stroke patients. Subjects must score  $\geq 24$  on the MMSE in order to qualify. [REDACTED]

[REDACTED] The Investigator will also determine their ability to rank pain based on interactions during the screening process or prior medical interaction with the subject.

Subjects will then be given the Brief Pain Inventory Short Form to determine their baseline degree of pain. Subjects will be instructed to focus on their shoulder pain when answering the BPI and must rate their worst pain in the last week as  $\geq 4$  on the BPI3 numeric rating scale to qualify for the study.

As a safety precaution to prevent potential excessive bleeding, subjects on warfarin will have blood drawn to confirm an INR of  $<3.0$ . If the INR is not below 3.0, subjects will be given the opportunity to have their warfarin dosage adjusted and the INR will be retested up to two additional times. The INR must be collected within 48 hours prior to the SPR Trial Stage procedure. In addition, a pregnancy test will be conducted in females of reproductive potential.

Once a subject has met all eligibility criteria, the Subject ID will be assigned.

During this visit, subjects will also be assessed for Pain-Free Range of Motion, complete the SF-36v2, complete the BDI-II, and be provided with an Economic

Impact Survey for completion at home. The SULCS and the QST testing (optional) will also be completed at this visit for subjects enrolled following the integration of these tests into the protocol.

Information regarding baseline pain medications (including type, dosage, and frequency) will be collected from the subject and/or their caregiver during this visit. Medications will be categorized as to whether they are used to treat shoulder pain or other types of pain. Subjects will be asked to control these pain medications. They will be instructed that dosages of pain medications should be maintained or can be decreased from their baseline dosage during the week prior to each study visit and phone call for the duration of their study participation. Thus, subjects will be asked to not increase their medication dosages above their baseline dosage during the week prior to each study visit and phone call for the duration of their study participation. The 1-week period was selected because the primary endpoint, BPI pain intensity, asks subjects to recall their worst pain in the past week.

Due to the frequency of visits during the Trial Stage, this medication protocol asks subjects to maintain or decrease their dosages throughout the duration of the Trial Stage. For pain medications that are taken on an as needed basis (e.g. "PRN"), subjects will be queried at baseline for their highest "as needed dose". Future "as needed" dosages during the week prior to the study visits and phone calls should not exceed this dosage.

If pain medication for breakthrough shoulder pain or other types of pain is required beyond their baseline dosage, this will be documented and analyzed in accordance with Sections 6.1 and 6.2.

#### **4.5.2 SPR Trial Stage**

##### **4.5.2.1 SPR Trial Stage Procedure/Start of sham period (Visit 2)**

Following the baseline visit, subjects will return to the clinic for the SPR Trial Stage Procedure. During the SPR Trial Stage procedure, a Smartpatch Lead will be placed. At the conclusion of this visit, the sham period will begin for each subject.

To determine a suitable location for placement of the Smartpatch Lead, [REDACTED]

[REDACTED]

[REDACTED]

Prior to leaving the clinic, subjects and their caregivers will be instructed on the proper care of the percutaneous lead exit site. To initiate the 3-week sham period, the Smartpatch Stimulator and Smartpatch Pad will be connected to the Smartpatch Lead (via the Smartpatch Lead Connector). The Investigator will then program the stimulator to deliver sham stimulation (i.e., no stimulation), which is further described in the SPR Clinician Manual. [REDACTED]

The subject will be instructed on how to turn stimulation on/off and how to connect and disconnect the Smartpatch Stimulator, Smartpatch Pad, Smartpatch Cable, Lead Connector Tapes, and adhesive bandages. The subjects will be instructed to use the Smartpatch Stimulator for a total of 6 hours each day.

Subjects will be blinded to this sham period

Subjects will also be instructed that they may or may not feel some of the stimulation levels.

Data regarding the specific details of the SPR Trial Stage procedure will be collected during this visit. In addition, the SPR Trial Stage procedure may be video taped for educational and training purposes. Subject faces will not appear in the video and each subject will sign a separate video consent (if applicable at the Investigational Site) if they agree to be video taped.

A detailed description of the SPR Trial Stage procedure and programming instructions, including instructions for Sham Programming Mode, for the Smartpatch System is provided in the Clinician Manual.

#### **4.5.2.2 48-hour Post-Lead Placement Safety Check (Visit 3)**

In order to mitigate the potential risk of infection, subjects will return to the clinic for a check of the Lead exit site within 48 hours of the SPR Trial Stage procedure. The exit site will be examined for any signs of early infection. If any signs of infection are observed, the subject will be provided with appropriate treatment, including possible removal of the percutaneous lead. Please refer to details regarding the proper disposition of subjects who develop an infection in Section 4.2.2.1.

#### **4.5.2.3 1-week Sham (Telephone Call #1)**

Subjects will be contacted via telephone 1-week following the start of the sham period. During this telephone call, subjects will be queried for pain intensity (BPI3), adverse events, and medication usage. Subjects will also be asked to select between two statements related to the effectiveness of subject blinding. These statements are further described in Section 4.5.2.5.

#### **4.5.2.4 2-week Sham (Telephone Call #2)**

Subjects will be contacted via telephone again 2-weeks following the start of the sham period to query for pain intensity (BPI3), adverse events, and medication usage. Subjects will also be asked to select between two statements related to the effectiveness of subject blinding. These statements are further described in Section 4.5.2.5.

#### **4.5.2.5 End of Sham Period/Turn Trial Stimulation ON (Visit 4)**

Three weeks following the SPR Trial Stage procedure (Visit 2) and at the conclusion of the sham period, subjects will return to the clinic for evaluation. Primary and secondary endpoints will be evaluated including the BPI, Pain Free Passive Range of Motion, SF-36v2, the Patient Global Impression of Change scale, and the BDI-II. The SULCS, and QST testing (optional) will be administered to subjects for which baseline SULCS and QST data are available, specifically, subjects who were enrolled after the incorporation of these tests into the protocol. The skin will be checked for evidence of infection. Subjects will also be queried for medication usage and adverse events. To assess participant compliance with the stimulation regimen, [REDACTED]

[REDACTED] will be recorded in the subject records. At the conclusion of the visit, the effectiveness of subject blinding will be evaluated by asking subjects to select the statement that best describes their experience in the past week: 1) I think stimulation was on some or all of the time during my daily stimulation sessions; 2) I think stimulation was off during my daily stimulation sessions. In order to be classified as blinded, a subject must respond that stimulation was on at least once during the sham period. A subject will be classified as not blinded if they respond that stimulation was off three times during the sham period (indicating that they did not believe stimulation was on at any time).

During this visit, the Investigator will [REDACTED]

[REDACTED] to begin the 3-week trial stimulation regimen. Stimulation parameters will initially be programmed based [REDACTED] identified during SPR Trial Stage procedure. If necessary, adjustments will be made to these parameters, [REDACTED]

[REDACTED]. Subjects will then be sent home with stimulation turned on and will be reminded of the proper use of the Smartpatch stimulator and continued care of the Lead exit site.

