Subjects will use the Smartpatch System for 6-weeks during the Trial Stage. To evaluate the placebo effect, the first 3-weeks of the SPR Trial Stage consist of a sham period in which the SPR Trial Stage device (i.e., the Smartpatch System) is placed, but stimulation is not delivered. Subjects are told that stimulation during lead placement may feel different than stimulation therapy. [REDACTED]

[REDACTED] Subjects will be blinded to the fact that stimulation is not being delivered. Following the sham period, stimulation will be delivered, and subjects will receive stimulation for a total of 6 hours each day for 3 weeks. Subjects will be queried for pain intensity on a weekly basis during the SPR Trial Stage using the BPI Short Form Question #3 (BPI3), and subjects will be instructed to focus on their shoulder pain when answering the BPI. Pain intensity at the end of the sham period will be compared to baseline pain intensity score to evaluate the placebo effect. At the conclusion of the SPR Trial Stage, subjects achieving at least a 2-point reduction on the BPI3 will receive monthly follow-up calls for up to six months in order to determine eligibility to advance to the SPR Implant Stage. During the Implant Stage, subjects will receive the fully implantable SPR Implant Stage system and be followed for three years.

All primary and secondary endpoints will be assessed at baseline and again at the completion of the sham period and the SPR Trial Stage. In addition, primary endpoints will be evaluated at all phone calls during the Trials Stage follow-up period and at all follow-up intervals during the SPR Implant Stage (3-weeks, 6-weeks, 12-weeks, 6-months, 9-months, and 12-months post IPG Stim ON). In addition, long-term follow-up will be conducted on an annual basis at 24-Months and 36-Months IPG Stim On.

Primary efficacy of the Trial Stage therapy will be determined at the end of the Trial Stage. Primary efficacy of the Implant Stage will be determined at the 12-week post-IPG Stim On follow-up visit. A subject will be considered a Trial Stage Success if he/she achieves at least a 2-point reduction in post-stroke shoulder pain intensity score in the BPI Pain Intensity Question #3 (BPI3) at the end of the Trial Stage (Visit 5) relative to end of the placebo period or baseline (Visit 4 or Visit 1), whichever is lower OR reports a BPI3 score of zero at the end of the Trial Stage.

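### The Visit 4 blinding question is timed for the end of the visit at which active stimulation is switched on, so the answer about the last sham week may come after the subject has felt it

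*Combined protocol and SAP*

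**What the plan says.** Blinding is checked three times in the sham period: at Telephone Call #1, at Telephone Call #2 and at Visit 4 (Sections 4.5.2.3 to 4.5.2.5). Section 4.1 states the aim: "Subjects will be blinded to the fact that stimulation is not being delivered".

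For Visit 4, Section 4.5.2.5 gives the timing: "At the conclusion of the visit, the effectiveness of subject blinding will be evaluated by asking subjects to select the statement". There are two options: that stimulation was on for some or all of the time, or that it was off. Subjects are to choose the one "that best describes their experience in the past week", and the week in question is the third sham week.

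The classification rule follows: "In order to be classified as blinded, a subject must respond that stimulation was on at least once during the sham period". A subject is not blinded only if all three answers are 'off'.

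The next paragraph of the same section covers the start of active therapy within the same visit. Programming is covered in a sentence that begins "Stimulation parameters will initially be programmed based"; its basis comes from the lead-placement procedure (part of the sentence is blacked out), and adjustment is allowed if needed. The paragraph ends: "Subjects will then be sent home with stimulation turned on". The Trial Stage schedule (Table 5) has the entry "X-Terminate sham" in its stimulation and programming row, but gives no order of steps within a visit.

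**The concern.** A check of belief during sham should be made before the subject has active therapy to compare it with. The cover story relies on subjects not knowing what therapy feels like: Section 4.1 says they are told that stimulation at lead placement may differ from therapy, and Section 4.5.2.1 that some levels may not be felt. Programming at Visit 4 can supply the missing comparison.

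The study has no randomized control, and the sham period is its means of judging placebo response. The Visit 4 BPI3 score is the reference for Trial Stage and Implant Stage success unless pain rose during sham (Sections 5.4.1.2 and 5.4.1.4, Table 9). BPI3 asks for worst pain in the last week, so the Visit 4 blinding answer is the only one that covers the same week as that score. If it is given after switch-on, it may not show what the subject believed when the score was formed.

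**Working it through.** The plan states no figure for blinding, so there is nothing to reproduce. The check has two parts: the order of steps, then what the rule does with a Visit 4 answer that has been influenced.

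**Order of steps**

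- The question is tied to the end of the visit, while programming and switch-on happen during it. On the plain words, the question follows switch-on.
- Section 4.5.2.5 refers separately to the end of the sham period in its opening sentence, but does not use that reference to time the question.
- Elsewhere, similar end-of-visit phrases mark a closing step: in Section 4.5.2.1 the start of sham after lead placement, and in Section 4.5.3.8 the change in daily hours after the assessments.
- No legible sentence requires the question to come before switch-on.

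**What the rule does**

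Inputs: 45 Trial Stage subjects (Synopsis, Number of Subjects) and the three-'off' rule (Section 4.5.2.5). Assumed, because the documents give no values: q, the probability of 'off' at each call; q4, the probability of 'off' at Visit 4; and independence of the three answers.

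- Share whose class depends on Visit 4 = P('off' at both calls) = q × q.
- Share classed as not blinded = q × q × q4.
- If Visit 4 is asked before switch-on and behaves like the calls, q4 = q and the share is q × q × q.

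| q | Depends on Visit 4: q² (of 45) | Not blinded, q4 = q (of 45) | Not blinded, q4 = 0.1 (of 45) | Not blinded, q4 = 1.0 (of 45) |
|---|---|---|---|---|
| 0.3 | 0.09 (4.05) | 0.027 (1.2) | 0.009 (0.4) | 0.09 (4.05) |
| 0.5 | 0.25 (11.25) | 0.125 (5.6) | 0.025 (1.1) | 0.25 (11.25) |
| 0.7 | 0.49 (22.05) | 0.343 (15.4) | 0.049 (2.2) | 0.49 (22.05) |

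The last two columns show a strong push towards 'on' and a complete push towards 'off'. At q = 0.5 the not-blinded count could move from 5.6 down to 1.1 or up to 11.25.

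**Dependence between answers**

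These figures are not bounds. Two cases at an overall 'off' rate of 0.5 show why:

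- Suppose 75% of subjects answer 'off' exactly twice, each order equally likely, and the rest never do (0.75 × 2/3 = 0.5). Nobody is then truly classed as not blinded. Those 'off' at both calls are 0.75 / 3 = 0.25. Turning all Visit 4 answers to 'off' adds 0.25 × 45 = 11.25 subjects, against 11.25 − 5.625 = 5.625 under independence.
- Suppose each subject gives the same answer every time. A push towards 'off' then changes no one's class.

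**The case against.** The strongest reply is that the section, read as a whole, points to the other order. The question and the classification rule stand with the sham evaluation, after the outcome measures, and switch-on comes in the next paragraph. The rule also counts answers given during the sham period, which fits a Visit 4 answer taken before sham ends. This stands as evidence of intent. It does not settle the matter, because the sentence that sets the timing is fully legible and refers to the visit. With up to five sites, practice could differ.

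Second, parts of the programming text are blacked out and the detailed instructions are in a Clinician Manual outside these documents. This also stands: the documents do not establish that subjects feel stimulation in clinic before they are asked.

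Third, the direction of any bias is unknown. Subjects had already met some stimulation at lead placement, and the question is explicitly about the past week. A reader might infer that a late question measures recognition of the switch and inflates the not-blinded count. The documents support only that the answer may be distorted, in either direction.

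Fourth, blinding class enters no success definition in Section 5.4.1 and no analysis listed in Section 6. Placebo response is also examined directly, through the Visit 4 against baseline comparison (Section 5.4.1.1) and the sham against stimulation comparison (Section 6.1.2.1). This limits the consequence, although neither comparison shows what subjects believed.

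**Conclusion.** The point holds as a defect in a stated timing rule. On its plain words, Section 4.5.2.5 allows the last blinding question to be asked after active stimulation has been turned on, and nothing legible prevents it. The Visit 4 answer decides the class of every subject who answered 'off' at both calls: 9%, 25% or 49% under independent answers with an 'off' probability of 0.3, 0.5 or 0.7. Those probabilities and the independence are assumptions made for illustration.

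A reader might go further and infer that the answers certainly follow switch-on, that the sham failed, or that the Visit 4 reference score and the success rates are invalid. The documents support none of these. The order is not spelled out step by step, Calls #1 and #2 are unaffected, and the success endpoints are computed without the blinding answer. What is weakened is the blinding assessment and, through it, the interpretation of the sham period and of the Visit 4 reference score. The correction should be made, but the primary analysis does not depend on it.

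**What to change.** In Section 4.5.2.5, replace the timing phrase that opens the blinding sentence with: *After the BPI and other outcome measures are completed, and before sham mode is ended, the stimulator is reprogrammed or any stimulation is delivered*. Asking after the outcome measures keeps the order already printed and avoids priming the pain score; the new element is the requirement to ask before sham ends. Make the same change on any visit worksheet.

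For subjects already seen, report the Visit 4 answers separately from those at Calls #1 and #2.

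The cost is one sentence in the protocol, a worksheet line and one extra tabulation. No visit, endpoint or treatment step changes.

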#### **4.5.2.6 1-week Trial Stim ON (Telephone Call #3)**

Subjects will be contacted via telephone 1-week following the start of the trial stimulation. During this telephone call, subjects will be queried for pain intensity (BPI3), adverse events, and medication usage.

#### **4.5.2.7 2-week Trial Stim ON (Telephone Call #4)**

Subjects will be contacted via telephone again 2-weeks after the start of trial stimulation to query for pain intensity (BPI3), adverse events, and medication usage.

